3.0 STUDY REFERENCE INFORMATION

3.1 List of Abbreviations

λ_z	terminal elimination rate constant
AE	adverse event
█	█
ALT	alanine aminotransferase
AST	aspartate aminotransferase
AUC	area under the plasma concentration-time curve
AUC ₂₄	area under the plasma concentration-time curve from time 0 to 24 hours
AUC _∞	area under the plasma concentration-time curve from time 0 to infinity
AUC _t	area under the plasma concentration-time curve from time 0 to the last quantifiable concentration
AUC _τ	area under the plasma concentration-time curve over the dosing interval (τ)
BMI	body mass index
CL/F	apparent clearance after extravascular administration
CL/F _{ss}	apparent clearance after extravascular administration at steady state
█	█
c_{max}	maximum observed plasma concentration
C_{min}	minimum observed plasma concentration
CNS	central nervous system
CS	clinically significant
CSF	cerebrospinal fluid
ECG	electrocardiogram
eCRF	electronic case report form
FDA	Food and Drug Administration
█	█
FSH	follicle-stimulating hormone
FT4	free T4
GCP	Good Clinical Practice
GGT	γ -glutamyl transferase
HBsAg	hepatitis B surface antigen
hCG	human chorionic gonadotropin
HCV	hepatitis C virus
HED	human-equivalent dose
ICF	informed consent form
ICH	International Council on Harmonisation
IEC	independent ethics committee
INR	international normalized ratio
IRB	institutional review board
K ₂ EDTA	dipotassium ethylenediamine tetraacetic acid
LFT	liver function test
MAD	multiple-ascending dose

MedDRA	Medical Dictionary for Regulatory Activities
MRSD	maximum recommended starting dose
NCS	not clinically significant
NOAEL	no-observed-adverse-effect-level
Ox1R	orexin 1 receptor
Ox2R	orexin 2 receptor
PK	pharmacokinetic
PRL	prolactin
PT	preferred term
PTE	pretreatment event
QTcB	QT interval with Bazett's correction method
QTcF	QT interval with Fridericia's correction method
RNA	ribonucleic acid
RO	receptor occupancy
SAE	serious adverse event
SAD	single-ascending dose
SAP	statistical analysis plan
SOC	system organ class
SRG	Safety Review Group
SUSARs	suspected unexpected serious adverse reactions
$t_{1/2z}$	terminal elimination half-life
TEAE	treatment-emergent adverse event
t_{max}	time to reach C_{max}
ULN	upper limit of normal
V_z/F	apparent volume of distribution after extravascular administration
V_z/F_{ss}	apparent volume of distribution after extravascular administration at steady state
WHO	World Health Organization

4.0 INTRODUCTION

4.1 Background

The neuropeptide orexin, also known as hypocretin, is produced exclusively in the orexigenic neurons in the hypothalamus. There are two forms of orexin, Orexin-A and orexin-B that are alternatively spliced from the same gene, HCRT. There are two orexin receptors, orexin 1 receptor (Ox1R) and orexin 2 receptors (Ox2R), both of which are G-protein coupled receptors. Both orexin-A and orexin-B can bind to either receptor and in each case, agonist binding results in an increase in intracellular calcium levels. However, while orexin-A is equipotent at both receptors, orexin-B shows a 10-fold selectivity for Ox2R.

Ox1R is selectively expressed in key brain areas relating to psychiatric disorders. Ox1R-expressing neurons in the bed nucleus of the stria terminalis, amygdala, locus coeruleus, raphe nucleus, and the ventral tegmental area are important in regulating emotions of stress, anxiety, motivation, and reward. CVN766 is a potent and highly selective small-molecule Ox1R antagonist with no significant off-target activity. Nonclinical PK and toxicology studies with CVN766 and other Ox1R antagonists have established their pharmacological characteristics and probable safety profile.

Ox2R is expressed in some overlapping areas, including the raphe nucleus, ventral tegmental area, but also areas important to arousal and sleep regulation, including the tuberomammillary nucleus.

The widely used sleep aid suvorexant (Belsomra[®]), approved for use in Australia, is a dual Ox1R and Ox2R antagonist, but its sleep-inducing effects are generally attributed to its activity on Ox2R. A second dual Ox1R and Ox2R antagonist, lemborexant, appeared safe and effective in clinical studies, has been approved in many countries worldwide, and has been submitted for marketing authorization in Australia.

Clinical effects to be expected of a selective Ox1R antagonist remain uncertain. CVN766 has not yet been studied in humans. Other selective Ox1R antagonists have reported early-stage human clinical trials, notably JNJ-61393215 (ClinicalTrials.gov Identifier: NCT04080752; Salvadore *et al.*, 2020) and ACT-539313 (NCT01954589; Kaufmann *et al.*, 2020; Kaufmann *et al.*, 2021). Both drugs were well tolerated and deemed safe for investigational use, the most common AEs being somnolence and mild headache.

4.2 Rationale for the Proposed Study

CVN766 is a highly selective orexin-1 receptor (Ox1R) antagonist and may have utility as treatment for psychiatric disorders including schizophrenia, panic disorder and anxiety, and addiction. Its safety and PK profile have been preliminarily established in nonclinical toxicology studies. The present study will be the first conducted in humans with CVN766 and will examine the compound's safety, tolerability, and PK in healthy subjects.

Nonclinical pharmacology, toxicity, and pharmacokinetic (PK) studies support the proposed escalating single- and multiple-dose study of CVN766 in healthy subjects with a starting dose of 5 mg. Section 6.2 outlines the justification for the planned dose ranges.

5.0 STUDY OBJECTIVES AND ENDPOINTS

5.1 Objectives

5.1.1 Primary Objective

To characterize the safety and tolerability profile of escalating dose levels of CVN766 suspension when administered as a single oral dose or daily oral doses for 7 days in healthy subjects.

5.1.2 Secondary Objectives

- To characterize the single-dose PK profile of CVN766 in plasma, and CSF
- To characterize the multiple-dose PK profile of CVN766 in plasma, and CSF
- To assess the effect of food on the bioavailability of CVN766 in the current formulation

5.1.3 Exploratory Objectives

- To explore possible drug metabolic enzyme and transporter polymorphisms that may contribute to variability in CVN766 PK, pharmacodynamics, or safety

5.2 Endpoints

5.2.1 Primary Endpoints

The primary endpoints of this study will be the following:

- Percentage of subjects who experience at least one treatment-emergent adverse event (TEAE)
- Percentage of subjects with abnormal and clinically significant (CS) safety laboratory test results at least once post-dose
- Percentage of subjects with abnormal and CS electrocardiogram (ECG) test results at least once post-dose
- Percentage of subjects with abnormal and CS vital sign measurements at least once post-dose

5.2.2 Secondary Endpoints

- Single-dose plasma PK parameters of CVN766 including time to maximum plasma concentration (C_{max}), area under the plasma concentration-time curve from time 0 to 24 (AUC_{24}) and time 0 to infinity (AUC_{∞}), and terminal elimination half-life ($t_{1/2z}$)

- Multiple-dose plasma PK parameters of CVN766 including C_{max} , AUC from time 0 to the end of dosing interval, $t_{1/2z}$, accumulation ratio, time to steady-state, steady-state C_{max} , and steady-state C_{min}
- Single-dose and multiple-dose CSF concentrations and CSF: plasma ratios of CVN766

5.2.3 Additional Endpoints

- Change from baseline in safety laboratory and ECG test results and vital signs
- Additional plasma PK parameters of CVN766 ie, CL/F and V_z/F

[figure not shown]
- Characterization of metabolic enzyme and transporter polymorphisms

6.0 STUDY DESIGN AND DESCRIPTION

6.1 Study Design

This is a phase 1, randomized, double-blind, placebo-controlled, single- and multi-dose ascending study in healthy subjects. [Figure 1](#) provides a schematic illustration of the study.

Figure 1 CVN766-101 Study Schematic

6.1.1 Part 1: Single-Dose Regimen and Fasted-Fed Crossover

Approximately 40 subjects will be enrolled in 1 of the 5 single-dose cohorts (designated as S1 through S5, respectively) in an ascending fashion. Dose escalation will only occur after a fully blinded review of all available safety, tolerability, clinical laboratory results (minimally including samples collected from subjects through 72-hours post-dose), and available PK data, including at least a 72-hour follow-up of the most recent cohort.

The planned dose levels are provided in [Table 5](#). Each cohort will consist of 8 subjects randomized to CVN766 or placebo, whereby 6 subjects will receive a single dose of CVN766 and 2 subjects will receive a matching placebo under overnight fasted conditions.

Sentinel dosing (1 subject to receive CVN766 and 1 subject to receive placebo) will be used in each cohort to ensure adequate safety and tolerability evaluation prior to administering CVN766 to the remainder of subjects within the cohort. After blinded review of 24-hour post-dose safety and tolerability data, the remaining 6 subjects of each cohort may be dosed provided that the adverse event (AE) profile of CVN766 in the first 2 subjects is considered acceptable.

Subjects for all cohorts will be admitted to the study unit 1 day prior to dosing and remain in the unit for safety and PK assessments at least 72 hours after dosing. On Day 1, subjects will undergo safety monitoring (including labs, physical exam, abbreviated neuro exam, cardia telemetry at 12-hours pre-dose) and PK sampling from blood plasma through 72 hours post-dose. In addition, for cohort S3 (fasted) only, from CSF via lumbar puncture at 3 hours post-dose. For subjects participating in the SAD cohorts, the total confinement period will be 4 nights unless extended for management of AEs at the discretion of the Investigator. Follow-up assessments will occur on approximately Days 8 and 14.

To assess the effect of food on bioavailability of CVN766 in suspension formulation, single-dose administration will be repeated in a single cohort after ingestion of a standardized high-fat high-calorie meal according to FDA Guidance for Industry (Food-effect bioavailability and fed bioequivalence studies, Dec 2002). Once the safety of the S3 cohort dose level has been assessed, the S3 cohort subjects will return to the clinic (no sooner than 14 days after their prior dose, or at least 4 half-lives has lapsed based on preliminary PK data, whichever is longer) and will receive the same dose as before, administered after ingesting a standardized breakfast. Subjects will finish the entire content of their breakfast within 25 minutes and will receive an investigational product 30 minutes (\pm 5 minutes) after beginning the meal. Sentinel dosing will not be required for subjects returning to the clinic for the fed regimen. If the CVN766 PK parameters in the fasted S3 cohort reveal poor absorption with inconclusive results, the fed cohort will be deferred until a higher dose level.

An outline of the single-dose study visit schedule is included in [Table 1](#). A Schedule of Study Procedures is listed in [Appendix A](#).

Table 1 Single-Dose Visit Schedule

Screening ^a	Inpatient Check-in	Dosing, PK, CSF & Safety Assessments ^b	Inpatient PK & Safety Assessments	Inpatient Discharge ^c	Follow-Up Outpatient Visit	Follow-Up Call ^d
Day -28 to -2	Day -1	Day 1	Day 2-4	Day 4	Day 8 \pm 1 day	Day 14 \pm 2 days

- (a) Screening will occur at study entry. Subjects returning for the “Fed” repetition of the single-dose regimen will not undergo Screening assessments except as required at Day -1.
- (b) CSF collection will apply only to cohort S3 (fasted).
- (c) Discharge from the clinic may be delayed if necessary to continue monitoring for resolution of AEs.
- (d) The final follow-up assessment will occur by telephone unless abnormal CS findings are observed upon discharge. In these cases, subjects must return to the clinic for re-evaluation.

6.1.2 Part 2: Multiple-Dose Regimen

For the multiple-dose regimen, approximately 24 subjects will be enrolled in 1 of the 3 multiple-dose cohorts (designated as M1 through M3, respectively) in an ascending fashion. Dosing will be administered in the fasting state; this can be changed by the SRG if exposure is found to be higher in the fed state. The dose levels planned to be studied in the multiple-dose regimen (M1 through M3) are provided in Table 5. Each multiple-dose cohort will consist of 8 subjects randomized to CVN766 or placebo, whereby 6 subjects will receive a daily dose of CVN766, and 2 subjects will receive matching placebo for 7 days. However, the duration may be increased to ≤14 days at the discretion of the safety review group (SRG) if preliminary PK data suggest steady-state will not be achieved within 6 days of daily dosing. Unlike the single-dose regimen, sentinel dosing within cohorts is not required in the multiple-dose regimen.

Subjects for all multiple-dose cohorts will be admitted to the study unit 1 day prior to dosing and remain in the unit for the duration of the dosing period and for at least 48 hours after the last dose for safety and PK assessments before discharge. On treatment Days 1 and 7, subjects will undergo safety monitoring and PK sampling from blood plasma through 48 hours post-dose and, in cohort M1 only, from urine through 24 hours post-dose. In cohorts M1 and M2, on treatment Day 7 (or last day of dosing, if extended beyond Day 7), subjects will additionally undergo PK sampling from CSF via lumbar puncture at 3 hours post-dose. If needed to resolve questions arising from prior cohorts' data, subjects in cohort M3 also may, at SRG discretion, undergo PK sampling from CSF via lumbar puncture, the choice of day (e.g., Day 1 or Day 7) and sampling time to be decided by SRG. Subjects in MAD cohorts may be asked to return to the clinic for an additional plasma PK sample 3 days after the last dose (e.g., Day 10) depending on emerging PK data, i.e., $t_{1/2}$. The total confinement period will be 9 nights unless extended for additional dosing days or for management of AEs. Follow-up assessments will occur approximately 7 and 14 days after the final dose. A summary of multiple-dose study visits is included in Appendix A.

Table 2 Multiple Dose Visit Schedule

Screening	Inpatient Check-in	Dosing, PK, CSF, & Safety Assessments ^{a,f}	PK / Safety Assessments & inpatient discharge ^b	Follow-Up Visits ^c	Outpatient Follow-Up Call ^d
Day -28 to -2	Day -1	Days 1-7 ^c	1 and 2 days after last dose (e.g. Days 8-9)	3 days ±0 after last dose (e.g. Day 10) & 7 days ± 1 after last dose (e.g. Day 14)	14 days ±2 after last dose (e.g. Day 21)

(a) CSF sampling will occur on Day 7 in cohorts M1 and M2. Cohort M3 also may, at SRG discretion, undergo PK sampling from CSF, the choice of day and sampling time to be decided by SRG.

(b) Discharge from the clinic is planned for Day 9 but may be delayed for additional dosing days or if necessary, to continue monitoring for resolution of AEs.

(c) If emerging PK data indicate the CVN766 $t_{1/2}$ is 15 hours (or less), the visit 3 days after the last dose (e.g., Day 10) may be omitted at Investigator's discretion.

(d) The Follow-up Visit will occur by telephone unless abnormal CS findings are observed upon discharge. In these cases, subjects must return to the clinic for re-evaluation.

(e) Dosing duration may be increased to ≤14 days at the discretion of the SRG based on preliminary PK and projected time to steady-state.

(f) Urine sampling will occur on Day1 and Day 7 in cohort M1.

6.1.3 Dose Escalation

The SRG will be comprised of the Investigator, Medical Monitor, Cerevance Responsible Medical Officer and may include other Cerevance representatives. A pharmacokineticist and other subject matter experts may participate as needed. The SRG will be responsible for ongoing review of safety, tolerability, clinical laboratory results, and available PK data and deciding to:

- Expand each single-dose cohort from the sentinel cohort to the full cohort (based on a review of at least 24 hours post-dose safety data from each of the sentinel subjects),
- Escalate to the next planned cohort or alternative dose levels (e.g., lower, intermediate, or higher) in single-dose cohorts (based on a review of available data including at least 72 hours post-dose safety data and clinical laboratory results from each of the subjects in the current cohort),
- Escalate to the next planned cohort or alternative dose levels (e.g., lower, intermediate, or higher) in multiple-dose cohorts (based on a review of available data including at least 48 hours post 7th dose safety data from each of the subjects in the current cohort),
- Add additional dose cohort(s) in either the single- or multiple-dose studies,
- Increase the duration of dosing in the multiple-dose cohorts from 7 days to ≤ 14 days

If 2 or more subjects in a single cohort experience the same type of serious or medically adverse event, further dosing will be withheld until the SRG investigates the events. Based on this assessment, the SRG will determine if the study should be terminated or continued and whether modification of planned dose levels and/or implementation of additional safety monitoring is indicated.

For each cohort (including sentinel subjects, where applicable), the SRG will carefully review the available blinded safety, tolerability, clinical laboratory results, and PK data to determine whether dosing should stop or continue (and, if continued, at what dose, including whether to repeat the previous dose), whether additional sequential dosing should be implemented in future cohorts or whether the blind should be broken to identify whether the subjects received CVN766 or placebo. However, precautions must be taken not to unblind the study staff, including the investigator.

If all doses are tolerated, then additional cohorts with higher doses may be considered; The actual choice of the subsequent dose level will occur after the full review of the available blinded safety, tolerability, clinical laboratory results, and available PK data in the preceding cohort. The subsequent dose level may be higher, lower, or remain the same as the preceding dose level. If necessary, additional cohort(s) may be added to fully characterize the safety and tolerability of CVN766.

Initiation of the multiple-dose regimen will only occur after a full blinded review of all available safety, tolerability, and clinical laboratory results for the fasting drug administration to single-dose Cohort S3 (minimally including samples collected through Day 4) and available PK data. For each multiple-dose cohort after the first, the actual choice of dose level may be modified by the SRG after review of the available blinded safety, tolerability, and clinical laboratory results and PK data in the preceding multiple-dose and next-higher-dosage single-dose cohorts (i.e., multiple-dose Cohort M2 will not initiate until the data review for multiple-dose Cohort M1 and single-dose

cohort S4 is complete). Each subsequent dose level may be higher, lower, or remain the same as the preceding dose level.

Additional multiple-dose cohort(s) may be added if deemed necessary by the SRG to fully characterize the safety and tolerability of CVN766. Such additional cohorts will follow the same schedule of events as for prior multiple-dose cohorts. Additional/Alternative PK timepoints may be implemented if the SRG determines this is necessary to fully characterize the PK profile of CVN766.

All AEs reported during the Treatment Period, both within and across cohorts, up to the time of discharge, will be evaluated to assess the need for the subject and/or study termination in accordance with the prespecified criteria for discontinuation/termination (Section 6.3.1).

Additionally, the SRG may decide not to escalate the dose for a particular cohort but rather administer the same or a lower dose level to the next cohort. Additional/ Alternative PK timepoints may be implemented if the SRG determines this is necessary to fully characterize the PK profile of CVN766.

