- (c) If emerging PK data indicate the CVN766 $t_{1/2}$ is 15 hours (or less), the visit 3 days after last dose (e.g., Day 10) may be omitted at Investigator's discretion.
- (d) The Follow-up Visit will occur by telephone unless abnormal, clinically significant (CS) findings are observed upon discharge. In these cases, subjects must return to the clinic for re-evaluation.
- (e) Dosing duration may be increased to \leq 14 days at the discretion of the SRG based on preliminary PK and projected time to steady-state.
- (f) Urine sampling will occur on Day1 and Day 7 in cohort M1.

Safety Review Group (SRG)

The SRG will be comprised of the Investigator, Medical Monitor, Cerevance Responsible Medical Officer and may include other Cerevance representatives. A pharmacokineticist and other subject matter experts may participate as needed. The SRG will be responsible for ongoing review of safety, tolerability, and clinical laboratory results, and available PK data and deciding:

1. Expand each single-dose cohort from the sentinel cohort to the entire cohort (based on a review of at least 24 hours post-dose safety data from each of the sentinel subjects),
2. Escalate to the next planned cohort or alternative dose levels (e.g., lower, intermediate, or higher) in single-dose cohorts (based on a review of available data including at least 72 hours post-dose safety data and clinical laboratory results from each of the subjects in the current cohort),
3. Escalate to the next planned cohort or alternative dose levels (e.g., lower, intermediate, or higher) in multiple-dose cohorts (based on a review of available data including at least 48 hours post 7th dose safety

data from each of the subjects in the current cohort),
 
4. Add additional dose cohort(s) in either the single- or multiple-dose studies,
 
5. Increase the duration of dosing in the multiple-dose cohorts from 7 days to ≤ 14 days,
 
In addition, if 2 or more subjects in a single cohort experience the same type of serious or medically significant event, further dosing will be withheld until the SRG investigates the events. Based on this assessment, the SRG will determine if the study should be terminated or continued and whether modification of planned dose levels and/or implementation of additional safety monitoring is indicated.
	

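### The multiple-dose escalation minimum is fixed to the 7th dose and does not move if dosing is extended up to 14 days

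*Protocol*

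**What the plan says.** Protocol Section 6.1.3 lists what the SRG decides and on what data. Escalation between multiple-dose cohorts needs a review "including at least 48 hours post 7th dose safety data from each of the subjects in the current cohort". The SRG list in the synopsis (Section 2.0) has the same minimum: "based on a review of available data including at least 48 hours post 7th dose safety".

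The same list lets the SRG lengthen multiple dosing from 7 days to no more than 14. Section 6.1.2 gives the trigger, "if preliminary PK data suggest steady-state will not be achieved within 6 days of daily dosing", and Table 2 footnote (e) leaves the extension "at the discretion of the SRG based on preliminary PK and projected time to steady-state".

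Other items in Section 6.1.2 do follow the last dose. Subjects stay in the unit "for at least 48 hours after the last dose for safety and PK assessments before discharge", CSF is taken "on treatment Day 7 (or last day of dosing, if extended beyond Day 7"), and follow-up is counted from the final dose. Some items stay at Day 7: the plasma PK schedule in Sections 6.1.2 and 9.1.10, and Table 2 footnotes (a), "CSF sampling will occur on Day 7 in cohorts M1 and M2", and (f).

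Section 6.1.2 also states that "sentinel dosing within cohorts is not required in the multiple-dose regimen".

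**The concern.** The escalation minimum is a safety rule in a first-in-human study. For a 7-day cohort it falls at the end of the 48 h inpatient observation after the last dose, so the next cohort opens only after a completed regimen has been seen. The rule names the 7th dose rather than the last one, so that guarantee weakens with each added day of dosing and then disappears.

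Followed to the letter in an extended cohort, the rule would let the next cohort start while the current one is still being dosed. That cohort receives 2.8 times the dose (M1 to M2) or twice the dose (M2 to M3), with no required sentinels. What would go unreviewed is the later part of the dosing period and all observation after it.

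**Working it through.** **Inputs.** Once-daily dosing, 7 days planned and up to 14 allowed (Sections 6.1.2, 6.1.3). Escalation minimum of 48 h after dose 7 (Section 6.1.3). Extension if steady state is not expected within 6 days, i.e. 144 h (Section 6.1.2). Projected animal half-life up to 6.5 h and a maximum clinical dose of 1670 mg/day (Section 6.2). Multiple doses of 45, 125 and 250 mg (Table 5).

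**The protocol's own point.** Dose 7 is given 6 × 24 = 144 h after dose 1, so the minimum is met at 144 + 48 = 192 h, which is Day 9. For 7-day dosing this is the planned discharge day.

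**Extended dosing.** The last dose of an N-day regimen is at 24(N − 1) h, so observation after the last dose when the minimum is met is 192 − 24(N − 1). The Day 9 dose falls at the same time as the minimum, so for N of 9 or more the doses still to give are N − 9 (Day 9 dose taken) to N − 8 (not yet taken).

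| Dosing days | Last dose (h) | Observation after last dose when minimum is met (h) | Doses still to give |
|---|---|---|---|
| 7 | 144 | 48 | 0 |
| 8 | 168 | 24 | 0 |
| 9 | 192 | 0 | 0–1 |
| 10 | 216 | −24 | 1–2 |
| 12 | 264 | −72 | 3–4 |
| 14 | 312 | −120 | 5–6 |

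A negative value means the minimum is met that many hours before the last dose.

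**How likely is extension?** The protocol does not define steady state. If it means 5 half-lives, the trigger is a half-life above 144/5 = 28.8 h. If it means 90% of steady state, it is above 144/log2(10) = 43.3 h. These are 28.8/6.5 = 4.4 and 43.3/6.5 = 6.7 times the upper animal value.

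**How much exposure would be unseen?** Assume one compartment, linear kinetics and dosing every 24 h. The fraction of steady state after n doses is then f(n) = 1 − 2^(−24n/half-life). When the minimum is met, dose 8 has been given and observed for 24 h, so the comparison is with f(8). The half-lives are assumed: 29 and 43 h are the trigger values, and 60 and 84 h show the range beyond them.

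| Half-life (h) | f(10)/f(8) − 1 | f(12)/f(8) − 1 | f(14)/f(8) − 1 |
|---|---|---|---|
| 29 | 0.7% | 0.9% | 1.0% |
| 43 | 2.6% | 3.7% | 4.3% |
| 60 | 5.2% | 8.2% | 9.9% |
| 84 | 8.4% | 14.1% | 17.9% |

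Near the trigger, the gap is mainly unreviewed duration and post-dosing observation. Extra exposure matters only at half-lives well above it.

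**Dose steps.** 125/45 = 2.8 and 250/125 = 2.0. The top planned dose is 250/1670 = 15% of the stated maximum.

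**The case against.** The strongest reply is that this is shorthand. The multiple-dose schedule in Appendix A heads its columns by last dose, with Day 7 only as the example, and has a column that serves as a model for added dosing days. Table 2 does the same for the two days after dosing. On that reading, 48 h after the 7th dose just means two days after the last dose. This is probably what was intended. It also shows that the escalation rule was not written to match: it names a fixed dose and makes no allowance for extension.

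The second reply is that the rule is a minimum and not a trigger. The SRG must still decide to escalate on the data available, and Section 6.1.3 holds M2 until the M1 data review is complete. Calling a review complete with doses still to give would be a strained reading. It is true that the SRG may wait, and the same group decides both extension and escalation. But data from doses not yet given are not available data, and the only stated content for the review is the 7th-dose minimum. The sentence on evaluating AEs up to discharge concerns termination of a subject or the study, not escalation.

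The third reply is that the consequence is small, and this stands. Extension is unlikely, and the extra exposure near the trigger is 1% to 4%. Each multiple dose is first studied or exceeded as a single dose (Section 6.2), and the hold rules in Section 6.3.1 operate across cohorts. A signal late in an extended cohort could still stop the next one.

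**Conclusion.** The point holds and is minor. The written minimum is correct for the planned 7-day regimen and does not contradict another clause. If dosing is extended, it no longer guarantees review of the completed regimen: the guaranteed observation after the last dose falls to 24 h at 8 days and 0 h at 9 days, and for 10 to 14 days the minimum is met 24 to 120 h before the last dose.

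The timing result follows from the protocol's own numbers. The judgement that extension is unlikely rests on the animal half-life carrying over to humans and on the assumed definition of steady state. The exposure figures rest on the one-compartment linear model. No endpoint or final safety analysis is affected.

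**What to change.** In Section 6.1.3 and in the synopsis SRG list, replace the 7th-dose wording with: *at least 48 hours of safety data after the last dose of the cohort's actual dosing period (Day 7, or later if extended)*.

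This changes one phrase in two places. Nothing changes for 7-day cohorts. In an extended cohort the earliest escalation moves to Day N + 2, so the next cohort opens N − 7 days later: 1 day for 8-day dosing, 3 for 10-day, 5 for 12-day and at most 7 for 14-day.
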